* Prior to the phone screen, participants will be asked to identify how they learned about the study and which site (UC or VA) they were referred from. Veteran participants may be seen at the Cincinnati VAMC or the UC Health Stress Center depending on their associated site. All civilian participants will be seen at the UC Health Stress Center.

D. Outcome Measures

The primary outcome is improvement in PTSD symptom severity as measured by clinically significant change on the Clinician-Administered PTSD Scale for DSM-IV or DSM-5 (CAPS-IV/CAPS-5).

A complete description of all of the outcome measures is in Appendix B.

E. Sample Size and Planned Statistical Analyses

1. Planned Statistical Analyses

The primary objective is to compare the effectiveness of CPT and ART in reducing the primary outcome -- PTSD symptom severity -- for Veteran and civilian patients with PTSD. We predict that CPT will be significantly superior to WL (and potentially superior to ART) in reducing PTSD symptoms post-treatment. To test this hypothesis we will use a 3 (Group: CPT, ART, WL) x 4 (Time: Baseline, Post-treatment) mixed-model ANCOVA covarying for baseline PTSD ratings. A significant omnibus interaction, and lower-order interactions, in the hypothesized direction will confirm this hypothesis.

The secondary objective is to compare the effectiveness of CPT and ART in reducing depression symptom severity. We predict that CPT will be superior to WL (and potentially ART) in reducing depression symptoms post-treatment. We will test this hypothesis with a mixed-model ANCOVA following the same analysis plan as for the primary objective.

The tertiary objective is to examine whether treatment effectiveness is reduced when patient preference for treatment is incongruent with their random assignment as we predict. To test this hypothesis, we will first categorize participants to a dichotomized preference group based on self-report. We will then perform a 2 (Group: Preferred Therapy, Non-preferred Therapy) x 4 (Time: Baseline, Post-Treatment, 3 Month, 1 Year) mixed-model ANCOVA covarying for baseline PTSD for both the primary (PTSD) and secondary (depression) outcome variables. A significant omnibus interaction, and lower-order interactions, in the hypothesized direction will confirm this hypothesis. Additionally, the primary and secondary analyses will be rerun covarying for preference to examine this variable's differential influence on CPT and ART outcomes.

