to identify PTSD symptom reductions over pre-and post-treatment in the WL condition considering the medium ES.

ES was small for active treatment difference between CPT and PCT symptoms post-treatment ($d = 0.16$). No data directly comparing CPT and ART are available in the extant literature. To detect a similarly small difference ($d_s < 0.2$) in PTSD severity means post-treatment with $\alpha = 0.05$, power = 0.80, two-tailed in the proposed study would require at least a total $N = 706$ ($n = 353$ for each active treatment). Therefore, the proposed $N = 240$ would be insufficient to identify statistically significant differences between CPT and ACT post-treatment if we assume a similarly small effect size. The extant literature does not provide ES estimates between CPT vs. WL and ART vs. WL, but these ESs would be expected to be considerably larger than the CPT vs. PCT estimate.

In the absence of prior WL data with which to estimate ES, and considering that we intend to test interaction effects primarily, we estimate the necessary sample size to detect statistically significant Time x Treatment interactions across the entire power and ES range. Results indicate that for the primary analysis we will have sufficient power to detect even small effects with a total sample size = 246 ($n = 123$ per active treatment condition). For the secondary analysis we will have sufficient power to detect even small effects with a total sample size = 138 ($n = 69$ per active treatment condition).

It should be noted that the above calculations are based on simple contrasts between means and hypothetical power functions for the interaction term in repeated measures ANOVA, none of which include covariates. **These estimates are conservative in that inclusion of covariates, as expected in the final analysis, generally increases power and we intend to over-sample minimally to accommodate participant attrition, further assuring adequate power. *The total sample, then, will be N = 240, split equally between the two active treatments.*** This estimate, based primarily on repeated measure ANOVA, is very conservative as it provides a sufficient sample size to detect even small interaction effects. If needed, we propose oversampling by up to 40 participants to account for drop-outs from assessment or to bolster marginal effects.

F. Random Assignment:

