[name], our statistician, has created a randomization table for all participants using a randomized, cross-over design. For participants who are randomized to the Wait List condition, following the completion of this seven week condition, they will be randomized into one of the two active treatment conditions, CPT or ART, using the randomization table (see Appendix C).

IV. Participant Characteristics and Recruitment

A. Inclusion Criteria

Participants will include 280 males and females ages 18 and older who meet criteria for PTSD (or subthreshold PTSD). Individuals will be included regardless of gender, ethnicity, military/civilian status, or type of trauma(s).

Participants must also agree to participate in either treatment, agree to allow IRB-approved study staff to access their medical record to review the extent to which they use UC or VA services before or during the study, have access to a telephone or agree to come into the Cincinnati VAMC, Trauma Recovery Center for the initial set of questions to determine whether they are eligible to participate, and agree to have their assessment and treatment sessions digitally audio recorded.

B. Exclusion Criteria

Participants who 1) meet criteria for unmedicated bipolar, mania, or unmedicated psychotic disorders; 2) meet criteria for a substance use disorder requiring detoxification treatment; 3) have active suicidal or homicidal intent with (a) plan(s) and (a) means; 4) have a medical condition that will interfere with twice weekly therapy sessions will be excluded from the research study; 5) show severe problems with memory or other problems with thinking and reasoning (defined as 1 SD below age-graded norms on the Montreal Cognitive Assessment [MoCA], Nasreddine et al. 2005).

Individuals with a psychotropic medication change within the last 30 days will be asked to stay consistent with their current dose for a minimum of 30 days before admission to the study.

C. Concurrent Treatment

Participants will be asked to refrain from any concurrent psychotherapy that focuses on treating the symptoms of PTSD or related mental health disorders. Exceptions will be made for those active in substance use treatment programs, including 12 step programs and relapse prevention.

D. Recruitment

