The participant must sign the ICF and the HIPAA Authorization (Cincinnati VAMC site only) before any study procedures are performed. A copy of the signed ICF will be given to the participant. The original signed forms will be filed in the Participant Consent Form Master File, which will be retained at each individual study site. For participant's at the UC Health Stress Center site, a copy of the signed ICF will be scanned into their medical records.

V. Assessments

A. Assessors: Clinical psychology post-doctoral fellows will perform all pre-, post-, and follow-up assessment interviews, and will be trained and supervised by licensed clinical psychologists. The assessors will remain blind to treatment condition throughout the study. Assessors will administer the: Clinician Administered PTSD Scale for DSM-IV and DSM-5 (CAPS-IV/CAPS-5), the Structured Clinical Interview for DSM-5 (SCID-5), the Montreal Cognitive Assessment (MOCA), and the Creative Imagination Scale.

Participants in the two active treatment conditions will complete a self-report assessment battery at pre-treatment, post-treatment, 3 month, and 1-year follow-up.

B. Self-Report Assessments: The self-report assessment forms will be completed by either paper-and-pencil questionnaires or the survey feature in RedCap. For assessments completed in RedCap survey, participants will complete the RedCap survey on a secure laptop computer or tablet at their designated location (connected to VA patient wifi at the Cincinnati VA or UC Health patient wifi at the UC Health Stress Center). Once a self-report survey has been completed by a participant, the RedCap system will not allow a participant access to change their responses. Participants will not have access to any data within RedCap, and will only be able to view their self-

report assessment forms in RedCap Survey mode. Table 2.0 indicates which self-report assessments can be completed by RedCap Survey and which assessments will be conducted by Assessor interview.

All potential participants will complete a pre-treatment assessment. Following their 7 week wait list period, participants in the WL condition undergo their first post-assessment. Their first post-assessment will be entered as their pre-treatment data when they are randomized to the active treatment condition. All participants will be reassessed in-person or by phone following treatment completion (post-treatment) and for their 3-month and 1 year follow-up.

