Assessment	Participant Payment (\$)
Baseline	70

Posttreatment*	75
3-month follow-up	85
1 year follow-up	100

*Individuals in the WL condition will receive two post-treatment assessments (one after WL period and one after completion of either CPT or ART following WL period), and will thus receive an additional \$75.00 for completion of the 2nd post-treatment assessment.

Participants randomly assigned to CPT or ART will receive up to \$330 in total compensation for their participation in this study. Participants randomly assigned to WL will receive up to \$405 in total compensation for their participation in the study.

Participants will be issued a debit card by the Greenphire ClinCard System. When a visit is completed funds will be approved and loaded onto the participants' card.

Participants will be issued one card for the duration of their participation. If a participant card is lost or stolen, they are instructed to call [contact]. An instruction sheet will be provided for further information. Greenphire and its Customer Support members will not have access to participant name or contact information; they will have a participant study ID number that will be provided to you by the study coordinator. Participants are able to use this study ID number to check the balance on their Greenphire debit card.

VII. Delivery of Therapy

A. Therapists: Two therapists at the UC Stress Center and 8 therapists at the Cincinnati VAMC, Trauma Recovery Center will perform all of the therapy. Therapists will be licensed clinical psychologists or licensed independent clinical social workers. Participants will be randomly assigned to therapist and then condition at both locations. Thus, all therapists will provide both therapies.

B. Training: [name] and three ART trainers will come to the Cincinnati VAMC for a 3-day ART training of the 10 therapists. [name] will ensure that therapists are appropriately trained in CPT.

C. Consultation: [name] and her team will provide weekly phone consultation in ART. All study therapists have already achieved CPT Provider status.

[name] will provide CPT consultation. Therapists will be approved as study therapists after [name] signs off on their abilities.

D. Digital Audio Recordings: All therapy sessions will be digitally audio recorded for later adherence review. See Data and Safety Monitoring section for more information.

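### The primary three-group model does not say whether re-randomised wait-list participants also count as CPT or ART, and the sample-size text does not separate randomised group size from the number per therapy

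*Combined protocol and SAP*

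**What the plan says.** Section III.E.1 tests the primary hypothesis with a "3 (Group: CPT, ART, WL) x 4 (Time: Baseline, Post-treatment) mixed-model ANCOVA covarying for baseline PTSD ratings". Four time levels are written but only two are named. The first prediction is that CPT beats WL; superiority to ART is only a possibility. The secondary (depression) objective is tested "following the same analysis plan as for the primary objective". The tertiary preference analysis has two groups and four named times.

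Section III.F says of WL participants that "following the completion of this seven week condition, they will be randomized into one of the two active treatment conditions, CPT or ART". Section V.B says of the visit after the wait: "Their first post-assessment will be entered as their pre-treatment data when they are randomized to the active treatment condition". The note to Table 3.0 says WL participants "will receive two post-treatment assessments (one after WL period and one after completion of either CPT or ART following WL period"). The Week 7 telephone script in Appendix A calls the visit after the wait a second pre-treatment assessment, and makes assignment to a therapy conditional on the participant still qualifying. Sections III and III.F state no such condition.

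Section III.E.2 gives, for the primary analysis, "total sample size = 246 ($n = 123$ per active treatment condition"), and for the secondary analysis, "total sample size = 138 ($n = 69$ per active treatment condition"). It concludes: "The total sample, then, will be N = 240, split equally between the two active treatments". Appendix C holds separate lists for the two sites, with an initial 1:1:1 allocation and a second 1:1 allocation of WL participants.

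**The concern.** Two analysts could follow this text and build different data sets. One would use the initial randomisation only: 240 people, one record each, 80 per group. The other would add the re-randomised WL people to CPT and ART, with the score after the wait as their baseline: 320 records from the same 240 people. Section III.E.1 fits the first as written. The equal split of 240 between two therapies and the double role of the visit after the wait point towards the second. No section decides.

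The choice bears on CPT-WL and ART-WL. If records are pooled, the same people stand on both sides of those contrasts, and part of each therapy group is observed after the wait instead of alongside it. The contrast is then no longer a purely randomised comparison of different people, and any natural course of symptoms can enter it. Nothing fixes the choice before the data are seen. The sample-size text adds to the doubt, because its figures per active treatment condition do not correspond to the groups of one consistent model.

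**Working it through.** **Counts from Appendix C.** Initial lists: VA 64/64/64 (192 rows), UC 16/16/16 (48 rows), so 80/80/80. Wait-list lists: VA 32/32, UC 8/8, so 40/40. Per therapy after re-randomisation: 80 + 40 = 120, of whom 40/120 = one third came through WL. Pooled records: 120 + 120 + 80 = 320.

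**The plan's sample sizes.** For a repeated-measures interaction with k groups and m times, lambda = f² × N × m / (1 - r), with df (k-1)(m-1) and (N-k)(m-1). The plan gives no f, r or power for this calculation. Assumed: f = 0.10, r = 0.5, power 0.80, alpha 0.05.

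| N | Design | lambda | Power |
|---|---|---|---|
| 246 | 3 groups x 2 times | 0.01 × 246 × 2 / 0.5 = 9.84 | 0.804 |
| 240 | 3 groups x 2 times | 9.60 | 0.793 |
| 138 | 2 groups x 4 times | 0.01 × 138 × 4 / 0.5 = 11.04 | 0.801 |
| 138 | 3 groups x 2 times | 5.52 | 0.537 |

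On these assumptions 246 is the smallest N for 3 x 2, with 246/3 = 82 different people per group. A 2 x 2 design needs 200 and a 3 x 4 design 174. The 3 x 2 figure depends on r: 486, 342, 246 and 150 at r = 0, 0.3, 0.5 and 0.7. The figure 123 equals 246/2 and also 82 + 41, the number per therapy once the 82 WL people are divided. The figure 138 (69 per group) matches the 2 x 4 tertiary preference analysis, not the three-group plan assigned to the secondary objective.

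**Effect of pooling on therapy-WL when therapy has no effect.** Assume unit SD, equal within-person correlation r, a natural fall a over the first period and a further fall b over the second. Lower scores are better, so a negative shift favours therapy.

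- ANCOVA on baseline. Directly randomised therapy and WL people both have adjusted outcome -a. People who came through WL start at -a and end at -a - b, so their adjusted outcome is -a - b + r × a. They differ from WL by r × a - b, and as one third of the arm they shift the contrast by (r × a - b)/3. Extremes: r = 0.3, a = b = 0.3 gives (0.09 - 0.30)/3 = -0.07; r = 0.7, a = 0.3, b = 0 gives 0.21/3 = +0.07.
- Change scores (equivalent to the two-time interaction). The shift is (a - b)/3: zero when a = b, and +0.10 when a = 0.3, b = 0.

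Simulated two-sided CPT-WL error at nominal 5%, with a = 0.2 or 0.3, b = 0 or a, and r = 0.3 to 0.7: about 6-11% pooled by ANCOVA and about 6-16% pooled on change scores, against about 5% for the initial randomisation only. With no natural course, overlap alone gives 5.2-6.0% by ANCOVA.

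**Price of the first-period contrast.** Detectable difference at 80% power = 2.80 × sqrt((1 - r²)(1/n1 + 1/n2)). At r = 0.5, 80 v 80 gives 2.80 × sqrt(0.75 × 0.0250) = 0.38 SD, and 120 v 80 gives 2.80 × sqrt(0.75 × 0.0208) = 0.35 SD. At r = 0.3 the pair is 0.42 and 0.39; at r = 0.7, 0.32 and 0.29. The 120 v 80 figure treats overlapping people as independent, so it flatters pooling.

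**The case against.** The strongest reply is that the plan never specifies pooling. The primary model as written fits the initial randomisation, Section V.B openly gives the visit after the wait two successive roles, and a payment note and a telephone script do not define an analysis set. CPT against ART, the primary objective, is untouched by the overlap, because each person contributes to only one therapy. All of this stands, and it limits the point to an unstated choice.

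Four stronger readings are tempting, and the documents do not support them.

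- That 123 is an error. It is the right count per therapy after re-randomisation (82 + 41), just as 120 is for 240. It is only not the group size behind 246.
- That the sections contradict each other on headcount. Sections III.E.2 and V.B and Appendix C agree through re-randomisation; Section III.E.1 is silent.
- That 138 shows WL was meant to be left out of the secondary analysis. It fits the plan's own tertiary design, so a labelling slip is the likelier explanation.
- That pooling favours CPT. The direction depends on the natural course and the model. In the settings above a change-score analysis shifts by zero or against therapy. ANCOVA favours therapy when the fall continues after the wait, and goes against it when the fall stops.

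The match of 246 to a three-group design also rests on assumed inputs; a 2 x 2 design gives 246 at r = 0.38. Nor is the first-period contrast guaranteed free of time effects: therapy is 5 to 15 sessions held once or twice a week, against a fixed 7-week wait. Its advantage is that it compares different people, as randomised.

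**Conclusion.** The point holds as a gap in pre-specification. Group membership in the primary model is undefined, and two defensible readings give different group sizes and different estimates of CPT-WL and ART-WL. The shifts and error rates above are conditional on natural falls and correlations that the documents do not give, and on the choice of model. They are small next to the pre-post effects of 1.04 to 2.02 quoted in Section III.E.2, so a large therapy effect would not be put in doubt; a marginal one could be.

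On the sample size, the total is sound under f = 0.10, r = 0.5 and power 0.80: the planned 240 has power 0.79 against 0.80 for 246. What needs correcting is the description. The group size in the three-group model is 82 (or 80), not 123, and 138 gives power of only about 0.54 for the three-group, two-time analysis assigned to the secondary objective. That objective is still covered by the planned 240 on the same assumptions.

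**What to change.** State in Sections III.E.1 and III.E.2:

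- (a) CPT-WL and ART-WL use the initial randomisation only, each person once (80 v 80).
- (b) CPT-ART uses everyone randomised to CPT or ART at either stage, once each, with the person's own pre-treatment score as baseline and entry stage (direct or through WL) as a stratum (up to 120 v 120). The Appendix C codes already link the two records (VJ8 and VJ8-2).
- (c) Site enters as a fixed effect, because the lists are built by site.
- (d) N = 246 means 82 per randomised group and 123 per therapy after re-randomisation; N = 240 means 80 and 120, with power 0.79 on the same assumptions. Give the f, r and power used, assign 138 to the analysis it serves, and correct the four time levels in the primary model, where two are named.
- (e) Reconcile the continued-eligibility condition in the Week 7 script with Sections III and III.F, and report the WL completers who are not re-randomised.

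No new visits or data are needed. The cost is wording, a site term and an entry-stage term, and a detectable WL difference of 0.38 instead of 0.35 SD at r = 0.5.

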The secondary objective is to compare the effectiveness of Cognitive Processing Therapy and Accelerated Resolution Therapy in reducing depression symptom severity.

C. Tertiary Objective

The tertiary objective is to examine whether treatment effectiveness is reduced when patient preference for treatment is incongruent with their random assignment.

D. Exploratory Analyses

Exploratory analyses will be performed to examine whether demographic (e.g., sex, age, Veteran/Non-Veteran status) and other clinically-relevant variables (e.g., sleep quality, anger, pain, health care utilization) predict differential response and/or drop-out across treatment condition.

III. Study Design

This study will examine the effectiveness of Cognitive Processing Therapy (CPT) as compared to Accelerated Resolution Therapy (ART) and a Wait list (WL) control using a Randomized, Cross-Over Design with blinded assessment. 280 participants will be randomly assigned to receive ART, CPT or WL condition. Upon completion of the WL condition after 7 weeks, participants will be re-randomized to ART or CPT.

The primary outcome is improvement in PTSD symptom severity as measured by change on the Clinician-Administered PTSD Scale for DSM-IV or DSM-5 (CAPS-IV/ CAPS-5) after treatment. This primary outcome measure will be administered by post-doctoral fellows in psychology who will remain blinded to treatment condition. The

CAPS-IV and CAPS-5 will be administered at pre- and post-treatment, and 3-month and 1-year follow-up visits.

A. Study Population

Participants will be 280 male and female Veterans and civilians who meet criteria for PTSD, or subthreshold PTSD, due to any Criterion A traumatic event. Subthreshold PTSD occurs when a patient has a Criterion A traumatic event, and endorses symptoms in each of the PTSD Diagnostic Criteria (B-E), but falls below the number and/or severity of total Criterion requirements to meet criteria for a PTSD diagnosis. Inclusion and exclusion criteria and recruitment are described in Section IV.

1. Rationale for Inclusion of Non-Veteran participants

Civilians will be included in this study as they have different Criterion A traumatic events (e.g., non-combat). It is imperative to the primary study objective to assess the comparative effectiveness of CPT and ART across a variety of trauma(s).

B. Study Treatment Conditions

1. Treatment Conditions

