Structured Clinical Interview for DSM-5 (SCID-5; First et al., 2015). Diagnoses for any co-occurring mental disorders will be made pre- and post- intervention by a trained post-doctoral fellow in psychology using the SCID-5, a structured clinician interview designed to assess for the presence of DSM-5 disorders and aid in differential diagnoses.

Expectancy of Therapeutic Outcome (Therapy Expectancy). This self-report assessment is completed a pre-treatment only, and assesses 4 participant expectancy-related thoughts about the treatment program they have been assigned (e.g., “how logical does this type of treatment seem to you?”). This measure has been used in prior PTSD clinical trials.

Treatment Preference. During the pre-treatment assessment, participants are given a brief overview of CPT and ART and are asked to indicate which treatment they prefer and how confident they are in their treatment preference on a 4-point Likert scale. This measure has been used in prior PTSD clinical trials.

Twenty-Item Toronto Alexithymia Scale (TAS-20; Bagby, Parker, and Taylor, 1994). This 20-item self-report measure assesses difficulty identifying feelings, difficulty describing feelings, and externally-oriented thinking. This measure has demonstrated good internal reliability ($\alpha = .81$) among a psychiatric sample.

Working Alliance Inventory-Short Revised (WAI-SR; Hatcher & Gillaspy, 2006). This 12-item revised and shortened version of the Working Alliance Inventory (WAI) is a measure of working alliance between therapist and patient in three areas: goal, task, and bond. This measure has demonstrated excellent total score internal reliability ($\alpha = .91 - .92$) and subscale internal reliability ($\alpha = .85 - .90$).

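### The preference test leaves out treatment, so a CPT-ART difference can pass as a preference effect or hide a real one

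*Combined protocol and SAP*

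**What the plan says.** Section II.C sets the tertiary objective: to "examine whether treatment effectiveness is reduced when patient preference for treatment is incongruent with their random assignment". Section III.E.1 gives the analysis. First, "we will first categorize participants to a dichotomized preference group based on self-report"; then a "2 (Group: Preferred Therapy, Non-preferred Therapy) x 4 (Time: Baseline, Post-Treatment, 3 Month, 1 Year) mixed-model ANCOVA" is fitted for PTSD and for depression, with baseline PTSD as the only covariate named. A significant interaction "in the hypothesized direction will confirm this hypothesis".

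The same paragraph adds that "the primary and secondary analyses will be rerun covarying for preference", with the aim of examining its "differential influence on CPT and ART outcomes". No treatment-by-preference term and no decision rule are given for that rerun.

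Appendix B says that at the pre-treatment assessment participants "are asked to indicate which treatment they prefer". The expected split is not stated. Section III.E.1 allows that CPT may be superior to ART. Section III.E.2 says no direct CPT-ART data exist and offers one active-versus-active figure: "ES was small for active treatment difference between CPT and PCT symptoms", with d = 0.16.

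**The concern.** Whether a participant is in the Preferred or Non-preferred group depends on two things: what they asked for and what they were assigned. Randomization makes assignment independent of preference, but it does not make the match groups alike in treatment. If 70% want therapy A, the matched group is 70% A and the unmatched group 30% A, so any difference between the therapies enters the contrast.

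If the popular therapy is also the better one, the plan can confirm that incongruence reduces benefit when it does not. If the popular therapy is the worse one, a real effect of incongruence shrinks or disappears. The confirmation rule is attached to this model, so the conclusion would depend partly on which therapy is more popular and which works better.

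**Working it through.** **Inputs from the document.** N = 240 in two equal active arms (III.E.2); four time points (III.E.1); alpha 0.05; d = 0.16 for CPT against PCT (III.E.2), used as a proxy for CPT-ART.

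**Assumptions.** Share p preferring one therapy: 0.6 to 0.8. Within-person correlation rho: 0.5, range 0.3 to 0.7. A larger therapy difference of D = 0.4. Compound symmetry, no attrition, and a difference that is zero at baseline and constant at the three later visits.

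**The plan's own figures.** No sample size is stated for the preference test. The general formula is lambda = N f² m/(1-rho), for k groups and m times, with df (k-1)(m-1) and (N-k)(m-1). With f = 0.1 and rho = 0.5 (neither is printed):

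- k = 2, m = 4, N = 138: lambda = 138 x 0.01 x 4/0.5 = 11.04, power 0.801.
- k = 3, m = 2, N = 246: lambda = 246 x 0.01 x 2/0.5 = 9.84, power 0.804.

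Both totals in III.E.2 are recovered, so this method and rho = 0.5 are a fair basis.

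**Bias.** Let a share p prefer therapy A. The matched group is p on A and 1-p on B; the unmatched group is 1-p on A and p on B. With D the advantage of A over B and M the true match effect, the contrast is

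M + [p - (1-p)]D = M + (2p-1)D.

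**False positives (M = 0).** Let e = (2p-1)D. The centred squares of the profile (0, e, e, e) sum to 0.75e², so lambda = N(0.75e²/4)/(1-rho), which is 90e² at N = 240 and rho = 0.5, with df 3 and 714.

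| D | p | e (SD) | lambda | rejection, rho 0.5 | rho 0.3 to 0.7 |
|---|---|---|---|---|---|
| 0.16 | 0.7 | 0.064 | 0.37 | 7.2% | 6.6% to 8.9% |
| 0.16 | 0.8 | 0.096 | 0.83 | 10.3% | 8.7% to 14.3% |
| 0.4 | 0.6 | 0.08 | 0.58 | 8.6% | 7.5% to 11.2% |
| 0.4 | 0.7 | 0.16 | 2.30 | 21.6% | 16.3% to 34.3% |
| 0.4 | 0.8 | 0.24 | 5.18 | 45.3% | 33.2% to 68.9% |

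Simulation (6,000 trials per setting, 120 per arm, rho 0.5) gives 7.2%, 10.8%, 8.8%, 21.4% and 44.5% for the same rows, 5.0% at p = 0.5 and 4.9% at D = 0. At D = 0.4 and p = 0.7, false confirmation in the hypothesized direction is 21% if the majority prefer the better therapy and 0.2% if they prefer the worse.

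**Masking (M = 0.3 SD, majority prefer the worse therapy, rho 0.5).** Here e = 0.3 - (2p-1)D, with D taken as the size of the difference.

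| D | p | e (SD) | planned test detects | with treatment x preference |
|---|---|---|---|---|
| 0.16 | 0.7 | 0.236 | 44% | 57% |
| 0.16 | 0.8 | 0.204 | 34% | 45% |
| 0.4 | 0.7 | 0.14 | 17% | 57% |
| 0.4 | 0.8 | 0.06 | 7% | 45% |

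Simulation of the planned test agrees within about a point (45%, 33%, 17%, 7%).

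**The last column.** With treatment and stated preference coded ±1, their product is the match variable, so the interaction term estimates M without bias. Its correlation with treatment is 2p-1, so its variance grows by 1/[1-(2p-1)²] = 1/[4p(1-p)]: 1.04, 1.19 and 1.56 at p = 0.6, 0.7 and 0.8. Dividing lambda = 90 x 0.3² = 8.1 by 1.19 and 1.56 gives 57% and 45%. Simulated false positives with this term were 4.6% to 5.5%.

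**The rerun.** Stated preference entered only as a main effect was significant in 4.7% to 5.4% of simulated trials with a true match effect of 0.3 SD, so it does not detect incongruence.

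**The case against.** The strongest reply is that the same paragraph supplies the remedy. The primary and secondary models contain treatment, they are to be rerun with preference, and the stated aim is a treatment-by-preference question. If preference there means match status, the rerun adjusts for treatment. That reading is possible, but the text does not state it, no interaction term is named, and the confirmation rule belongs to the 2 x 4 model. Match status also has no value for wait-list participants while they serve as the control arm of the primary model. It becomes defined only after they are re-randomized to CPT or ART.

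Second, the size depends on a preference split and a therapy difference that the document does not give. At d = 0.16 the inflation is modest, and the large rates all come from D = 0.4, which is 2.5 times that figure. This stands.

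Third, the calculation omits the baseline covariate and attrition and holds the difference constant to one year, so the percentages are illustrations. This also stands, but including the covariate does not make the problem smaller. For the average of three post-baseline visits adjusted for baseline at rho = 0.5, the residual variance is 2/3 - 0.25 = 0.417 and the standard error is sqrt(0.417 x 2/120) = 0.083. At d = 0.16 the biases of 0.064 and 0.096 then give about 12% and 21% rejection (11% and 21% by simulation).

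Fourth, the correction costs power, and the objective is tertiary. Both are true; the primary and secondary comparisons of the arms are unaffected.

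**Conclusion.** The concern holds. The model that carries the confirmation rule for the preference hypothesis estimates the match effect plus (2p-1) times the CPT-ART difference, and the rerun as worded does not repair it. There is no bias if preferences split evenly or if the therapies are equal.

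At the plan's proxy of d = 0.16, false positives rise from 5% to about 7% to 10% for splits of 70:30 to 80:20. Detection of a true 0.3 SD effect falls from 66% to 44% or 34% when the majority prefer the worse therapy. At an assumed D = 0.4 the same splits give 22% to 45% false positives, and detection falls to 17% or 7%. The bias formula needs only 1:1 assignment independent of preference. The rates also rest on the assumed p, rho, D and covariance structure.

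**What to change.** For participants in active treatment, model the outcome on baseline, treatment (CPT or ART), stated preference and treatment x stated preference, each by time. Name the treatment x preference (x time) term as the test of the congruence hypothesis for PTSD and for depression, and attach the confirmation rule to it. In the rerun, use the same CPT-versus-ART x preference term and say whether preference means the therapy named or its match to assignment. Report the preference split by arm.

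This changes only the wording of section III.E.1: preference is recorded before treatment and assignment is known. The statistical cost is a variance increase of 4%, 19% or 56% at 60:40, 70:30 or 80:20. If CPT and ART do not differ, power for a true 0.3 SD match effect falls from about 66% to 57% at 70:30 and 45% at 80:20. The plan should state that power so that a null result on this objective is read accordingly.
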